Thirty days after hospital discharge, the participants' electronic health record will be reviewed to retrieve data about initial hospital length of stay and 30-day unplanned hospital readmission. Visit 3 will be performed at approximately 6 weeks post hospital discharge. This is the time at which some patients may begin more chemotherapy or radiation treatment (adjuvant therapy), and Visit 3 will be performed prior to this to avoid confounding effects of the therapy.

Exercise Intervention: Participants will start the exercise program within four weeks of their diagnosis and decision to undergo neoadjuvant treatment and continue until surgery. Participants will continue to receive the standard medical care (described below) provided at UCCC. Individual exercise sessions in this program implement a "whole body" approach and consist of a 10-min cardiovascular warm-up and 50 minutes of cardiovascular endurance, resistance, and flexibility exercises (session components). Typical cardiovascular endurance exercises include walking on an indoor track or treadmill, stationary cycling, and stationary rowing. Resistance training includes exercises using body weight, free weights, and weight machines targeting increased strength of the large upper and lower extremity muscle groups and core stability. Flexibility exercises target major muscle groups activated during the exercise. Target intensity of exercise will be based on the American College of Sports Medicine (ACSM) recommendations for cancer survivors²: 40-85% heart rate reserve for cardiovascular endurance exercises; 60-70% one repetition maximum for resistance exercises; and a rate of perceived exertion of 12-16 on a 6-20 Borg scale for all activities.

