Exercise Adaptations: Prior to the start of exercise sessions, participants will be questioned on significant changes in symptoms or the presence of new symptoms (such as nausea or fever), which will be used to modify the exercise session (intensity and components) for that day to allow maximum symptom-limited participation. Participants will be encouraged to complete three sessions per week for at least eight weeks during neoadjuvant therapy. Exercise intensity, components, and time will be recorded for each exercise session to guide the exercise specialist in making appropriate exercise adjustments (progression, maintenance, or reduction). Exercise programs have been found to be safe in cancer survivors, even during life-threatening treatments², but safety has not been investigated specifically in the current population. Common risks may include muscular fatigue and soreness, as well as transient increases in treatment-related symptoms. Rarer risks include the possibility of injury due to unknown bone metastases or acute cardiac events. Intensity and acute changes in symptoms will be closely monitored to decrease these risks.

Participants will schedule their sessions with the exercise specialists administering the program, typically taking place between 8AM and 4PM, Monday through Friday, at the

Anschutz Center for Health and Wellness. Adherence will be measured as the percent of scheduled sessions attended. Exercise sessions will also be individualized to participants on a day to day basis, with time and intensity not exceeding that listed above. Prior to the start of exercise sessions, participants will be questioned on significant changes in symptoms or presence of new symptoms (such as nausea or fever), which will be used to modify the exercise session for that day. Exercise intensity, type, and time will be recorded for each exercise session.

Standard Care: Participants in the Standard Care group will receive no exercise intervention, but will continue to receive standard follow-ups, treatments and services from their oncology team. The services that participants receive as standard care include their medical care, symptom control, social worker support, and nutrition.

Participants in all groups will receive \$50 reimbursement for each Visit completed, totalling \$150.00 for all three Visits.

D. Description, Risks and Justification of Procedures and Data Collection Tools:

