The timeline for this protocol is estimated at 2 years. Data collection (participant recruitment and intervention) is estimated at 1 - 1.5, after which data will be analyzed and manuscripts prepared.

Data Analysis and Anticipated Outcomes: Groups will be compared on demographic variables such as age and gender. Variables that differ significantly will be included in planned analyses as covariates. Statistical significance will be defined as $\alpha \leq 0.05$, however, results will be interpreted cautiously as is warranted for pilot studies⁴⁴. As we expect to be underpowered to test for statistical interactions, multiple tests will be used to assess differences in baseline measures, change scores, and postoperative outcomes between groups. Change scores will be calculated as the difference between Visit 2 and Visit 1. Groups will be compared using non-parametric exact k-sample permutation tests, which are well suited for small sample sizes as they do not rely on typical normal-theory methods⁴⁵.

Aim 1: The feasibility of implementing this intervention will be assessed by quantifying the accrual rate of patients willing and able to participate in the preoperative exercise intervention and individual patients' adherence to the prescribed exercise program (percentage of scheduled sessions attended). Safety will be determined by the number of non-serious and serious adverse events and relatedness of the events to exercise, as described by COMIRB.

Aim 2: Hypothesis 1 – Baseline physical fitness and function measures and change scores will be compared between groups using exact k-sample permutation tests. We anticipate a significant difference in the changes from Visit 1 to Visit 2, with the Exercise group demonstrating maintained or improved physical fitness and function compared to the Control group, with no differences in baseline measures. A secondary analysis will be used to describe the trajectory of changes in physical function from visits 1, 2, and 3.

Hypothesis 2 – Postoperative outcomes will be compared with exact k-sample permutation tests (hospital length of stay) or Fisher's exact tests (hospital readmission) between the Exercise and Control groups. We anticipate the Exercise group to have a significantly lower hospital length of stay and occurrence of hospital readmission compared to the Control group.

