Exploratory Aim: Hypothesis 1 – Baseline psychological stress and systemic inflammatory status measures and change scores will be compared between groups using exact k-sample permutation tests. We anticipate a significant difference in change scores, with the Exercise group demonstrating decreased (improved) psychological stress and improved systemic inflammatory status (decreased CRP, IL-6, sTNFR1 and IIS; increased IL-10) compared to the Control group, with no differences in baseline measures.

Hypothesis 2 – Spearman correlations will be performed between preoperative measures of psychological stress and systemic inflammatory status and postoperative variables. We

anticipate a significant negative correlation between psychological stress and systemic inflammatory status and postoperative outcomes, with lower levels of stress and inflammation associated with improved outcomes in all participants.

G. Summarize Knowledge to be Gained:

Aim 1: The feasibility of future, larger scale implementation of the preoperative exercise program will be assessed primarily by patient adherence to the program, demonstrating patients' ability and willingness to complete the program. The future study of the intervention will be assessed through the measurement of patient accrual, which will provide a reference for the necessary time frame of future studies.

Aim 2: The analyses performed in this aim will reveal 1) how a preoperative exercise intervention affects physical fitness and physical function prior to and after surgery, and 2) whether a preoperative exercise program is associated with improved postoperative outcomes in patients with pancreatic cancer undergoing neoadjuvant treatment. These analyses will also illustrate typical changes in measures of physical fitness and physical function through analysis of the Standard Care group.

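### Aim 1 scores adherence by attendance alone, which cannot by itself show the ability to complete the programme that section IV.G reads from it

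*Combined protocol and SAP*

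**What the plan says.** The definition appears twice and is the same both times. Section IV.C, Exercise Adaptations: "Adherence will be measured as the percent of scheduled sessions attended". Section IV.F, Aim 1: "individual patients' adherence to the prescribed exercise program (percentage of scheduled sessions attended". Aim 1 otherwise lists accrual and adverse events. It contains no measure of what was done within a session.

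Section IV.G says that the feasibility of larger-scale implementation will be "assessed primarily by patient adherence to the program, demonstrating patients' ability and willingness to complete the program".

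Section IV.C, Exercise Intervention, describes the session itself. Sessions "consist of a 10-min cardiovascular warm-up and 50 minutes of cardiovascular endurance, resistance, and flexibility exercises", with target ranges of 40-85% heart rate reserve, 60-70% of one repetition maximum and a Borg rating of 12-16.

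Under Exercise Adaptations, symptoms reported before a session are information "which will be used to modify the exercise session (intensity and components) for that day to allow maximum symptom-limited participation". The same part later says that sessions are individualised from day to day and that time and intensity may not go above those described. It gives no lower bound for a session to count as attended. The target is given in sessions: "Participants will be encouraged to complete three sessions per week for at least eight weeks during neoadjuvant therapy".

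The content of each session is recorded: "Exercise intensity, components, and time will be recorded for each exercise session to guide the exercise specialist". A second sentence further down repeats the recording, with type in place of components, and attaches no purpose to it.

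**The concern.** Attendance and performance are different quantities, and section IV.G asks one number to stand for both. Coming to a session is fair evidence of willingness. Whether the patient could do the endurance, resistance and flexibility work once there is a separate question. It matters in this trial because the patients are on neoadjuvant therapy, reductions for symptoms are provided for, and section III reports no preliminary studies of preoperative exercise in this population.

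Two conclusions are at stake. First, a high attendance figure could be carried into a larger study as evidence that the described session is tolerated, when it shows only that patients turned up. Second, if fitness does not differ between groups, attendance alone cannot help a reader separate an ineffective programme from one delivered at reduced content. Section IV.E tests the duration of exercise training as a covariate. In context that is the length of the training period; it does not describe session content and does not enter the adherence score.

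**Working it through.** The documents state no adherence result or threshold, so there is no figure to reproduce. The check asks how far attendance and delivered minutes can differ under the plan's own schedule.

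**Inputs**
- Full session: 10 + 50 = 60 minutes (IV.C, Exercise Intervention).
- Frequency: three per week (IV.C, Exercise Adaptations).
- Typical programme: 12 weeks (IV.E).
- Scheduled sessions: 3 × 12 = 36, assuming that the encouraged frequency is what gets scheduled. Full-session minutes: 36 × 60 = 2,160.
- Assumed attendance: 32 of 36.
- Assumed number of attended sessions cut to the 10-minute warm-up: *c* = 0, 8 or 16. The documents give no rate, so these values only show a range.

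**Formulas**
- Attendance = attended / scheduled = 32/36 = 88.9%, for every *c*.
- Minutes delivered = [(32 − *c*) × 60 + *c* × 10] / 2,160.

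**Results**

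| Attended sessions cut to warm-up | Attendance | Minutes delivered |
|---|---|---|
| 0 of 32 | 88.9% | 1,920/2,160 = 88.9% |
| 8 of 32 | 88.9% | (1,440 + 80)/2,160 = 70.4% |
| 16 of 32 | 88.9% | (960 + 160)/2,160 = 51.9% |

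The gap is 0, 18.5 and 37.0 percentage points. Counting only the 50-minute main part (36 × 50 = 1,800 minutes), 8 cut sessions give 24 × 50/1,800 = 66.7% and 16 give 16 × 50/1,800 = 44.4%.

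Delivered minutes are the product of attendance and the average share of a full session done when attending. With 8 cut sessions that share is 1,520/1,920 = 79.2%, and 88.9% × 79.2% = 70.4%. The plan reports the first factor and not the second.

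Minutes are only part of the matter. The clause on symptom-based changes names intensity and components, so a session may keep its length and still be reduced. A minutes figure would miss that, which is why the fix has a second measure.

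**The case against.** The other side has substantial points.

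- **Sixty minutes reads as a ceiling.** Sessions are individualised daily, and the stated limits run only upward. A patient who does all that is asked on a symptomatic day can fairly be said to have followed that day's prescription. The plan never says this outright, but it is a sensible reading, and it tells against redefining adherence as minutes divided by 60: that would score adaptation directed by the protocol as non-adherence. This stands.
- **The plan's own unit is the session.** The target is set in sessions per week, and attendance is openly defined. This stands as a reason to keep attendance, but it does not make attendance evidence of ability.
- **The data exist.** A reader might infer from the first recording sentence that the session records serve only to guide the specialist. The second sentence carries no such restriction, so nothing prevents their use. What is missing is a planned summary under Aim 1.
- **Extreme gaps are not predicted.** A reader might infer that 89% attendance could well sit beside less than a third of the exercise. Arithmetically that needs at least 25 of the 32 attended sessions (78%) cut to a warm-up, (7 × 60 + 25 × 10)/2,160 = 31.0%, or every attended session cut to 20 minutes, 32 × 20/2,160 = 29.6%. The documents give no modification rate and describe no warm-up-only session. Section IV.D also discontinues participants judged no longer physically capable of the intervention. Nothing supports that pairing as an expectation, least of all for the whole exercise group.
- **No stated decision turns on the figure.** There is no adherence threshold; the 70% rule in section IV.E concerns enrolment. Section IV.F promises cautious interpretation. This limits the consequence, but section IV.G still calls adherence the primary basis for judging feasibility.

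**Conclusion.** The point holds in a limited form. As defined, adherence supports a statement about willingness to attend. It does not, alone, support the statement about ability to complete the programme that section IV.G draws from it. Neither the training-duration covariate nor the discontinuation rule supplies the missing information.

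The size cannot be estimated from the documents. On the typical schedule, with 32 of 36 sessions attended, the gap between attendance and delivered minutes runs from zero to about 18 points if a quarter of attended sessions are cut to the warm-up, and to about 37 points if half are. These figures rest on assumed cut rates and on three sessions per week being scheduled. If few sessions are modified, attendance and delivered minutes will nearly agree, and reporting both would show it.

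This is an inexpensive improvement to what Aim 1 can conclude. It is not a defect in the exercise programme or in its adaptation to symptoms.

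**What to change.** Keep the percentage of scheduled sessions attended as the attendance and adherence measure in sections IV.C and IV.F. Add two descriptive summaries to Aim 1 in section IV.F, taken from the intensity, components or type, and time already recorded at each session:

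1. For each patient, minutes completed relative to full 60-minute sessions, labelled as exercise delivered and not as adherence. State whether the denominator is scheduled or attended sessions; the figures above use scheduled sessions.
2. The percentage of attended sessions completed with all components and within the intensity ranges of section IV.C, against the percentage modified for symptoms.

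In section IV.G, base the statement on ability to complete the programme on attendance and these two summaries together. Do not redefine adherence as minutes over 60. No session content, adaptation rule or procedure changes.

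The cost is wording, a little data entry and a short descriptive table. The reason for a modification is not among the items listed as recorded, so one extra field may be needed to identify symptom-related changes. The feasibility picture may look less favourable than attendance alone.

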The potential participant population will be individuals who receive a diagnosis of borderline-resectable pancreatic cancer (adenocarcinoma), being treated at the University Hospital Cancer Center. These inclusion and exclusion criteria will apply to participants in both groups.

Inclusion Criteria: Recent (< 4 week) first diagnosis of a borderline-resectable pancreatic adenocarcinoma, assigned to receive neoadjuvant therapy and surgery at University of Colorado Cancer Center, physician clearance to participate in exercise program, and age 21-80 years.

Exclusion Criteria: Any significant comorbid conditions that would interfere with or preclude participation in an exercise intervention, including orthopedic conditions such as advanced osteoarthritis, mobility-limiting amputations or chronic injuries, or mobility-limiting acute orthopedic injuries; advanced rheumatoid arthritis; widespread chronic pain conditions such as fibromyalgia; pulmonary conditions such as chronic obstructive pulmonary disease, emphysema, interstitial lung disease, use of supplemental oxygen; known cardiovascular disease, uncontrolled hypertension, or new cardiac event within the past 6 months. Participants with a second cancer diagnosis at the time of enrollment will be excluded.

Sample size estimation: No studies have previously investigated the effects of preoperative exercise in patients with pancreatic cancer. In patients with lung cancer, a preoperative exercise program reduced hospital length of stay by 4 days compared to usual care⁴⁰. Based on this difference, with a SD of 3, 12 participants would be required in each the experimental and control groups ($\alpha = 0.05$, $\beta = 0.90$ ⁴¹). To account for overall attrition, groups will be increased by 3 participants each, based on a study of preoperative exercise after neoadjuvant treatment in patients with rectal cancer showing an overall attrition of 28%⁴². A total of **30 participants (15 per group)** will be recruited for this study.

C. Study Design and Research Methods

This is a prospective, non-randomized, parallel group, intervention control trial, patterned on a similar pilot study in patients with rectal cancer⁴².

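### The fitness comparison uses change scores without adjusting for Visit 1, for a reason that does not apply with two visits; a baseline-adjusted analysis should be pre-specified beside it

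*Combined protocol and SAP*

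**What the plan says.** Section IV.F (Data Analysis Plan) defines change as Visit 2 minus Visit 1. For Aim 2, Hypothesis 1 it states: "Baseline physical fitness and function measures and change scores will be compared between groups using exact k-sample permutation tests". It anticipates no baseline differences and says nothing about what follows if some are found.

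The reason for separate tests is given just before: "As we expect to be underpowered to test for statistical interactions, multiple tests will be used to assess differences in baseline measures, change scores". That sentence goes on to include postoperative outcomes.

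Three places mention covariates:
- Section IV.F: demographic variables that differ significantly between groups.
- Section IV.E: durations of exercise training and of neoadjuvant therapy.
- Section IV.A: prior physical activity, as a possibility.

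None names the Visit 1 value of the outcome, and none says how a covariate enters a k-sample permutation test. Section IV.A makes 400-meter walk time the primary fitness outcome. Under Section IV.C, volunteers join the exercise group if willing to take part and the control group if practical barriers prevent it. Section IV.E accepts that selection bias and baseline differences may result.

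**The concern.** Two things look wrong. First, the stated reason does not lead to the chosen test: avoiding an interaction because of low power, and then testing change between groups, is the same test under another name. Second, Visit 1 is measured on everyone but used only by subtraction, which fixes its coefficient at 1.

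At stake is precision in a small study, and whether the fitness conclusion depends on an analysis choice the reader cannot see. Section IV.E says the results are meant to support later, adequately powered studies, so the walk-time estimate and its precision will be carried forward.

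**Working it through.** **Inputs.** From the documents: two visits in the hypothesis test, alpha 0.05, and 12 evaluable per group (Section IV.B). The documents give no effect size, SD or visit correlation r for any fitness measure. Values of r, the SD ratio and the baseline gap below are assumptions, shown over a range.

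**The plan's own figure.** Only length of stay is sized: "a preoperative exercise program reduced hospital length of stay by 4 days compared to usual care", and "with a SD of 3, 12 participants would be required in each the experimental and control groups". Two-sided, reading the printed 0.90 as power: n = 2 × (1.960 + 1.282)² × 3² / 4² = 11.8, so 12 per group. The figure reproduces. It says nothing about power for the 400-meter walk.

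**Interaction identity.** With two visits, the group-by-visit term is (mean Visit 2 − mean Visit 1) in the exercise group minus the same quantity in controls. That is the difference in mean change. In a simulated data set with 12 per group, both tests gave t = 1.5616, p = 0.1327 on 22 df.

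**Precision with comparable baselines.**
- Var(change) = SD1² + SD2² − 2r·SD1·SD2.
- Var(Visit 2 adjusted for Visit 1) = SD2²(1 − r²).
- Their difference is (SD1 − r·SD2)², which is zero when r·SD2/SD1 = 1.
- With equal SDs the ratio, adjusted to change, is (1 − r²) / [2(1 − r)] = (1 + r)/2.

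With the effect set to give the change score 80% power at 12 per group (t test and ANCOVA standing in for the permutation versions, separate simulation runs):

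| Assumed r | Variance ratio | Adjusted power |
|---|---|---|
| 0.4 | 0.70 | about 90% |
| 0.6 | 0.80 | 86–87% |
| 0.8 | 0.90 | 81–83% |

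At r = 0.9 the ratio is 0.95, but estimating the slope uses up the gain: the standard errors are 0.182 SD (change) and 0.181 SD (adjusted).

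Unequal SDs can also remove it. With r = 0.8, SD1 = 1 and SD2 = 1.25, Var(change) = 1 + 1.5625 − 2 = 0.5625 and Var(adjusted) = 1.5625 × 0.36 = 0.5625.

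**Precision with a baseline gap** (12 per group):

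| Gap | r | SE, change | SE, adjusted |
|---|---|---|---|
| 0.5 SD | 0.8 | 0.258 | 0.260 |
| 1 SD | 0.5 | 0.41 | 0.41 |
| 1 SD | 0.7 | 0.32 | 0.34 |
| 1 SD | 0.9 | 0.18 | 0.21 |

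**Bias with a baseline gap D, no treatment effect, equal SDs.**
- Groups regress to a common mean: the expected Visit 2 gap is rD. The change score is off by rD − D = −(1 − r)D; the adjusted difference is unbiased.
- The gap is stable: the expected Visit 2 gap is D. The change score is unbiased; the adjusted difference is off by D − rD = (1 − r)D.
- At D = 0.5 SD and r = 0.6 the size is 0.4 × 0.5 = 0.2 SD either way.

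Simulated false rejection at a nominal 5%, r = 0.5, 12 per group:

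| Gap | Model | Change | Adjusted |
|---|---|---|---|
| 0.5 SD | common mean | 9.3% | 5.0% |
| 0.5 SD | stable gap | 4.9% | 9.8% |
| 1 SD | common mean | 21% | 5% |
| 1 SD | stable gap | 5% | 22% |

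**Can the baseline test warn of this?** Chance alone gives the baseline difference a standard error of √(2/12) = 0.41 SD. A two-sample t test at 12 per group detects a 0.5 SD gap about 22% of the time and a 1 SD gap about 65%.

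**The case against.** The strongest objection is that adjustment is not clearly better in this design. A reader might infer that adjusting for Visit 1 always gives more power from the same data, and should therefore replace the change score. The documents do not support that. They give no r and no SDs, assignment is by willingness and circumstance, and Section IV.E foresees baseline differences. The gain can be nil or negative. A stable gap, which is plausible when groups form around transport or home location, biases the adjusted analysis and not the change score. This part of the objection stands.

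A reader might also infer that the plan ignores covariates, or that its interaction sentence is simply false. The plan does name covariates; what is missing is the Visit 1 outcome. The sentence does not say which interaction is meant. A three-visit interaction would be a different test on 2 df, and the sentence also covers postoperative outcomes. But Hypothesis 1 is tested on Visits 1 and 2, and Visit 3 enters only a descriptive secondary analysis. For that test the reason fails, and the sentence needs rewording rather than deletion.

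It is fair, too, that this is a pilot with feasibility as its first aim, that it promises cautious interpretation, and that no decision rule hangs on a fitness p-value. That limits the weight of the point. It does not explain why only one of two defensible analyses should be shown.

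**Conclusion.** The concern holds in a limited form. The identity between the two-visit change comparison and the group-by-visit interaction is exact, so the plan's reason does not support its choice. The omission of the Visit 1 outcome from the covariates is plain from the text.

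The possible gain is moderate and conditional: from 80% to about 90%, 87% or 81–83% power at r = 0.4, 0.6 or 0.8, given 12 per group, comparable baselines and similar SDs. The stronger argument is sensitivity. Either analysis can be off by (1 − r) times the baseline gap, under opposite assumptions that the documents cannot settle, so neither is safe alone. This is a worthwhile low-cost improvement, not a flaw that invalidates the plan.

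**What to change.** In Section IV.F, for the 400-meter walk first and then the other uncapped fitness and function measures:

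- Pre-specify a permutation test of group on the Visit 2 value adjusted for the same measure at Visit 1 (for example Freedman–Lane permutation of reduced-model residuals), alongside the planned change-score test.
- Report both group differences with 95% intervals. Treat a conclusion as robust only if the two agree, and define agreement in advance, for example the same direction and the same result at 0.05.
- State how the covariates already named in Sections IV.A, IV.E and IV.F enter the permutation analyses.
- Reword the interaction sentence so that it no longer justifies the change-score test.

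Single limb stance is capped at 30 seconds, which makes linear adjustment awkward, so it can stay with the change score.

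The cost is SAP wording and a little programming; the data are already planned. There are two downsides. Residual permutation is approximate, so the adjusted test gives up the exactness the plan chose. The two estimates may also disagree, in which case the report must say that the conclusion depends on the assumption about baseline differences. Agreement would not remove other confounding from self-selection.

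### Readmission: Fisher's exact test is valid but very conservative at the planned size; Boschloo's exact test gains power under the same 5% ceiling when group sizes are close to equal

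*Combined protocol and SAP*

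**What the plan says.** Section IV.F (Data Analysis Plan), Aim 2 Hypothesis 2, compares length of stay by permutation test and readmission by Fisher's "exact tests (hospital readmission) between the Exercise and Control groups". The level is set in the same section: "Statistical significance will be defined as $\alpha \leq 0.05". The stated expectation is: "We anticipate the Exercise group to have a significantly lower hospital length of stay and occurrence of hospital readmission compared to the Control group". Whether the tests are one- or two-sided is not stated.

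The study is sized on length of stay alone (section IV.B, Sample size estimation). The cited lung cancer result is that "a preoperative exercise program reduced hospital length of stay by 4 days compared to usual care", and then: "Based on this difference, with a SD of 3, 12 participants would be required in each the experimental and control groups". Three are added per group for attrition, giving 15 per group and 30 in all. Readmission is defined in section IV.A, but the documents give no expected rate and no power for it.

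Two other passages bear on the point. Section IV.E admits that the sample may be too small to show differences in postoperative outcomes, and section IV.F asks for caution in reading pilot results. Section IV.C describes the design: "This is a prospective, non-randomized, parallel group, intervention control trial". Willingness and practical barriers decide who is in which group, so the final split is not fixed.

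**The concern.** Fisher's test conditions on both margins of the 2x2 table. With few participants the conditional distribution has only a few possible values, so the largest attainable error rate below 5% is often far below it. The unused part of the 5% is lost power.

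Readmission is one of the two outcomes named in Aim 2 Hypothesis 2, and the plan looks for significance on it. If the chosen test uses less than half of the error rate the plan allows, some real differences will be missed because of the test, on top of those missed because the sample is small. Unconditional exact tests avoid much of this loss while still guaranteeing an error rate of at most 5%.

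**Working it through.** **Inputs.** From the documents: level 0.05; 12 evaluable and 15 recruited per group; Fisher's test. Assumed: a two-sided test; control readmission rates of 20% to 40% against 5% to 10% with exercise.

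**The plan's own figure.** For a 4-day difference, SD 3, two-sided 0.05 and 90% power (the printed β = 0.90 is read as power):

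n = 2 × (1.960 + 1.282)² × 3² / 4² = 11.8, so 12 per group.

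This matches the plan. A one-sided level would give 10, which is why two-sided is the working assumption.

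**Fisher's threshold at 12 v 12.** With k control readmissions and none with exercise, the two-sided p-value is 2 × C(12,k) / C(24,k):

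- k = 4: 2 × 495 / 10,626 = 0.093
- k = 5: 2 × 792 / 42,504 = 0.037

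So 5 v 0 is the smallest significant result against zero. The next boundaries are 7 v 1 and 8 v 2. At 15 v 15 the test still needs 5 v 0 (p = 0.042; 4 v 0 gives 0.0996).

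**Boschloo's test.** It uses Fisher's p-value as the test statistic. Its own p-value is the probability of a Fisher p-value at least as small, maximised over the unknown common rate. All 13 × 13 tables were enumerated, with the common rate on a grid of 1,999 points. At 12 v 12:

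| Control v exercise | Fisher p | Boschloo p |
|---|---|---|
| 4 v 0 | 0.093 | 0.045 |
| 5 v 0 | 0.037 | 0.017 |
| 6 v 1 | 0.069 | 0.029 |

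Every table rejected by Fisher's test is also rejected by Boschloo's.

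**Actual type I error at 12 v 12.** This is the sum, over the rejected tables, of the product of two binomial probabilities with the same rate.

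| Common rate | Fisher | Boschloo |
|---|---|---|
| 10% | 0.25% | 1.5% |
| 20% | 1.2% | 3.8% |
| 30% | 1.7% | 4.5% |
| 50% | 2.3% | 3.8% |
| Maximum over all rates | 2.3% | 4.5% |

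At 15 v 15 the maxima are 1.8% and 4.3%.

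**Power.** The same sum with different rates in the two groups:

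| Control v exercise rate | 12 v 12, Fisher | 12 v 12, Boschloo | 15 v 15, Fisher | 15 v 15, Boschloo |
|---|---|---|---|---|
| 20% v 5% | 4% | 12% | 8% | 19% |
| 30% v 10% | 9.5% | 20% | 15% | 26% |
| 30% v 5% | 16% | 32% | 27% | 43% |
| 40% v 10% | 23% | 38% | 33% | 46% |
| 40% v 5% | 36% | 55% | 52% | 67% |

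**Unequal splits of 24, at 30% v 10%.**

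| Exercise : control | Fisher | Boschloo |
|---|---|---|
| 14 : 10 | 11.0% | 20.8% |
| 10 : 14 | 9.1% | 18.3% |
| 16 : 8 | 16.5% | 17.2% |
| 8 : 16 | 3.5% | 15.7% |

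The threshold moves as well. With 14 exercise and 10 control, Boschloo rejects at 3 v 0. With 10 exercise and 14 control it needs 5 v 0.

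**The case against.** Fisher's test is valid, standard and pre-specified, and the plan already concedes low power for postoperative outcomes and asks for cautious reading. That stands: this is a matter of efficiency. The concession, however, puts the low power down to sample size. The part that comes from the test can be avoided, and section IV.F still expects significance.

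Sidedness is an assumption. A one-sided Fisher test at 0.05 would already reject at 4 v 0 (495 / 10,626 = 0.047), with power almost the same as two-sided Boschloo (19.7% under both at 30% v 10%). This also stands. The 5 v 0 threshold holds only for a two-sided test, and the plan should say which it means.

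The gain depends on the split. At 16 exercise v 8 control it is negligible, so a general promise of more power would be wrong.

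The two tests share a 5% ceiling, but their actual error rates differ. At a common rate of 20% the false-positive rate rises from 1.2% to 3.8%. That is the price of the extra power, and it stays within what the plan allows.

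A reader might infer that Fisher's test is an error, or that replacing it would make the readmission comparison adequately powered. The documents support neither. The test controls its error rate, and with Boschloo at 12 per group power is still only 12% to 55% over the rates tried. With self-selected groups, confounding remains the larger threat, and no choice of test addresses it.

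**Conclusion.** The point holds as a cheap improvement. Under a two-sided 0.05 test with 12 per group, Fisher's test leaves more than half of the permitted error rate unused (at most 2.3% of 5%). Boschloo's test recovers most of it and adds about 8 to 19 percentage points of power over the rates tried, roughly doubling it or more where the control rate is 20% to 30%. The same pattern holds at 15 per group.

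This rests on two-sidedness, on assumed readmission rates, and on groups of equal or nearly equal size. A non-significant readmission result would say little under either test.

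**What to change.** In section IV.F, Aim 2 Hypothesis 2:

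1. Replace Fisher's test for readmission with a two-sided Boschloo exact test at 0.05. Name the test and its sidedness in advance, because unconditional tests built on different statistics can disagree when groups are unequal.
2. Report the readmission risk in each group and the risk difference with an exact unconditional 95% confidence interval.
3. Replace the expectation of a significantly lower readmission rate with a statement that this comparison is mainly for estimation, because power is low under either test.
4. If a significance threshold is quoted, calculate it for the realised group sizes. Do not fix it at 4/12 v 0/12.

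The cost is a few lines of wording and a test available in standard software, with no extra participants or data. The actual false-positive rate will be higher than with Fisher's test, though still below 5%. Selection bias from the non-random assignment has to be handled separately.
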